## Protocol

### Abstract

**Objective:** Adolescents and young adults (AYA) living with chronic illnesses often struggle to adhere to daily oral medication regimens. Mobile health (mHealth) interventions are a promising avenue to support AYA in improving adherence, such as through delivering human coaching following the Supportive Accountability Model via mobile devices. AYA have reported increased use of and preference for text message communication over phone calls, so more investigation is needed to understand how cell phone support could be efficaciously delivered.

**Methods:** A randomized, controlled, 3-arm pilot trial will evaluate the impact of Cell Phone Support (CPS) on medication adherence. Conditions will be CPS delivered by phone calls (CPS-C), CPS delivered by text messages (CPS-T), or automated text message reminders (ATR). Participants will include AYA with various chronic illnesses (i.e., solid organ transplant, epilepsy, type 2 diabetes, sickle cell disease), aged 15-20 years ( $N = 60$ ). Randomization will be done via stratified blocks based on sex assigned at birth and focal diagnosis. Outcomes will include intervention engagement, participant satisfaction, and medication adherence, assessed using multi-method measurement. Additionally, focus groups will be used to assess the impact of CPS and understand how patients and healthcare providers experience the intervention.

### Research Background:

In the US, there are 2 million AYA living with chronic illness, many of whom struggle to develop vital illness self-management skills. Over half of AYA are nonadherent to their medication, resulting in detrimental health outcomes, increased healthcare expenditures, and poorer quality of life (Rapoff, 2010). Since over 95% of AYA use cell phones (Lenhart, 2015),

mobile health (mHealth) technology is a promising method for delivering self-management interventions. To date, several mHealth interventions have demonstrated efficacy for improving medication adherence in a cost-effective manner. Unfortunately, of the existing adherence-promoting mHealth interventions, nearly all suffer from the same significant limitation: they are disease-specific, which significantly limits the pace of implementation. A general, flexible mHealth intervention for AYA living with diverse chronic illnesses could meaningfully accelerate the timeline for implementation of adherence-promoting interventions in widespread practice.

CPS is an adherence-promoting mHealth intervention that has been piloted separately with AYA with HIV (Belzer et al., 2014) and solid organ transplants (Sayegh et al., 2018), showing evidence of efficacy for increasing medication adherence. The current version of CPS includes short phone calls (<5 minutes) made each weekday by a human coach to provide social support, medication reminders, problem-solving coaching, incentives for answering calls, and referrals to other services. CPS calls focus on assisting AYA in identifying and accessing resources and support from their natural environments, such as finding ways they can receive needed help from their families, peers, medical teams, and communities. Pilot results indicate that CPS may promote medication adherence in two very different medical conditions; however, participant feedback and study enrollment rates suggest adaptations are needed to improve the acceptability of CPS. Many pilot participants indicated they would prefer to receive CPS through text message conversations with the AF, instead of traditional phone calls. This finding is consistent with national trends in technology use and preference; in the past decade, AYA have reported believing text messaging is easier, faster, less socially awkward, and more confidential than talking on the phone (e.g., Evans, Davidson, & Sicafuse, 2013). Although some promising

two-way, interactive text message adherence interventions exist (e.g., Dowshen et al., 2012), all have been automated interventions, not live, real-time conversations between human Coaches and AYA patients.

Although AYA prefer texting, it is unknown how delivering CPS through this communication mode could impact its effect on adherence. What most distinguishes CPS from other mHealth interventions is that human Coaches deliver the intervention in real-time, live phone calls, in contrast to the automated reminders which have proliferated in the adherence literature. The Supportive Accountability Model provides a framework for understanding how technological aspects of mHealth could impact the provision of adherence-focused support [7]. This model describes how a positive bond with a credible, caring person creates a sense of accountability, which in turn increases engagement in health behaviors. Counterintuitively, text message interaction could enhance, rather than dilute, supportive accountability because individuals tend to make more positive attributions of their communication partners and engage in more self-disclosure when using “lean media” that does not include the voice of the communication partner (Mohr, Cuijpers, & Lehman, 2011). These findings, along with current AYA technology preferences and practices, suggest CPS may be more acceptable, feasible, and effective if delivered by live, real-time, interactive text messaging with human Coaches instead of traditional phone calls.

### **Research Aims:**

The aim of this randomized pilot trial is to evaluate the acceptability, feasibility, and efficacy of CPS delivered by phone calls or text messages to AYAs with several distinct chronic illnesses, in preparation for a fully-powered multisite, effectiveness-implementation hybrid trial. We propose 1) assessing the feasibility, acceptability, and efficacy of CPS for improving

medication adherence, 2) investigating the impact of delivering CPS through live text messages versus phone calls using quantitative and qualitative methods, and 3) evaluating patient and provider views of CPS to guide future implementation work. The proposed research follows the conceptual model (Figure 1), positing that CPS will promote adherence through engaging AYAs in calls or texts with a human coach providing social support. We predict that delivering CPS by text message will increase feasibility and acceptability, perceived social support, and medication compared to voice delivery. This study extends the literature on mHealth to promote AYA adherence in several ways. First, although increasingly interactive and personalized *automated* text message interventions are proliferating in the adherence literature, there have been no randomized trials published evaluating the impact of *live* text message conversations on medication adherence among AYA. Second, rather than focusing on a single focal diagnoses, this study will enroll AYA with *diverse* chronic illnesses. This approach could greatly increase the number of patients having access to self-management support, therefore leading to a greater reduction in negative healthcare outcomes, costs, and burden. Third, despite comprising over 20% of the US AYA population, Latinx patients make up only 5% of mHealth study samples (e.g., DeKoekkoek et al., 2015). The proposed study will enroll >50% Latinx participants, based on pilot data, increasing national representativeness of the mHealth iteration [4].

## **Methods:**

### **Setting and Sample**

This study took place at Children's Hospital Los Angeles (CHLA), a large, urban, quaternary care, free-standing children's hospital that services approximately 36,000 unique AYA patients and cares for nearly one-third of LA County's Title V beneficiaries. As a safety net hospital, CHLA serves the most vulnerable children in the community, many of whom are at

high risk for gaps in care and adverse outcomes as they transition to adulthood. Participants in this study including patients who met the following inclusion criteria: 1) 15-20 years old at enrollment, 2) a patient at CHLA, 3) taking at least one oral medication per day, 4) provider and patient agreement that medication adherence is currently <80%, 5) Access to a cell phone, and 6) ability to speak and understand English. Participants were excluded if they had a cognitive impairment that precluded them from engaging in the consent/assent process or study protocol. Participants with diagnoses of autism spectrum disorder or intellectual disability were eligible as long as they were able to describe the purpose of the study, risks and benefits of enrolling, and summarize the research procedures in their own words. Non-English speaking patients were excluded because interventions were only developed in English at this stage. In addition, health care providers were enrolled to participate in focus groups and interviews. For healthcare providers, inclusion criteria was: 1) Status as a healthcare provider at CHLA providing care to adolescent and young adult patients taking daily oral medication, and 2) working in a CHLA subspecialty clinics which had agreed to refer patients to this study.

## **Design**

After passing eligibility screening and completing pre-treatment questionnaires, participants will be randomly assigned (1:1:1) to one of three 12-week groups: CPS delivered through voice-based phone calls (CPS-C), CPS delivered through text messaging (CPS-T), or automated text message reminders (Automated Reminders). A research colleague outside of the team used rand( ) function in Excel to create randomization blocks of 6 by sex assigned at birth and focal diagnosis. I hope to prevent substantial confounding by using stratified block randomization. For example, among the first 6 female participants with organ transplants, 2 would be assigned to CPS-C, 2 would be assigned to CPS-T, and 2 would be assigned to ATR.

The research colleague placed cards in sealed envelopes indicating the group assignment, and after the participant signed the consent form, the PI opened the envelope and informed the participant of the group they had been assigned to.

## **Procedures**

This study was approved by the Children's Hospital Los Angeles Institutional Review Board. Adult patients provided informed consent, and parents provided permission and minor participants providing assent. Adult participants or parents of minor participants signed a waiver of HIPAA to participate in the study since text-messaging is not a HIPAA compliant form of communication. Surveys were administered via REDCap, with up to 3 invitations sent by text message over the course of one week, at pre-treatment (0 weeks), mid-treatment (6 weeks), post-treatment (12 weeks), and follow-up (18 weeks). Participants were compensated with a \$50 gift card for the pre-treatment surveys, and \$25 gift cards at each of the three followed assessment periods. Focus groups with participants were held in same-study-condition cohorts via WebEX after at least 2 participants had completed the 12-week intervention. Participants were compensated with a \$20 gift card for joining the focus group. Participants received a \$15 gift card for mailing back their MEMS Cap at 18 weeks. A community advisory board (CAB) consisted of  $N = 8$  18-24 year old current and former patients was recruited in June 2020. The CAB meetings bimonthly via WebEx to provide guidance and feedback on each stage of the research.

## **Interventions**

***Cell Phone Support.*** A human coach delivered CPS either by phone calls (CPS-C) or live, real-time, two-way text messaging (CPS-T), between 3-5 days per week for 12 weeks. Participants

were given the choice of the frequency of their calls/texts based on CAB guidance. Coaches were undergraduate research assistants earning course credit at the University of Southern California. They will participate in a single, 2-hour training on the promotion of medication adherence, with 1 hour of phone-based group supervision every 2 weeks throughout the trial, similar to the prior pilot studies of CPS [3,4]. Coaches were trained in delivering CPS through phone calls (CPS-C) and text messages (CPS-T), and delivered both CPS conditions. Each CPS interaction will last no more than 5 minutes, following the outline below. Participants received monthly incentives worth \$40 contingent upon answering over 75% of the Coaches calls or text messages. Examples of CPS call content from the organ transplant pilot study [4] include: 1) coaching patients to reach out to their social worker for assistance navigating insurance changes, 2) teaching patients how to use cell phone alarms to remind them to take medications, 3) supporting patients to identify ways a parent could help them wake up on time to take scheduled doses on weekend mornings, 4) assisting patients to devise strategies to link medication-taking with daily routines, e.g., brushing teeth, and 5) making referrals to family therapy when family conflict interferes with medication-taking. CPS is based on theories of social support, in that the COACHprovides support for adherence directly to the AYA patient while optimizing the support available from their natural networks, such as parents, peers, romantic partners, healthcare providers, or others.

Coaches were trained to refer patients to their providers during daytime hours or the physician-on-call during night hours if they make medical complaints, ask about their health status, or express confusion about their prescribed medications. Healthcare provider and CAB feedback indicated that it is important for physicians to have accurate knowledge of patients' medication adherence in order to monitor health and safety, and adjust medication dosages effectively. To ensure that health care providers can monitor and follow-up on adherence issues

impacting health, we will alert them to patients' nonadherence, whether disclosed in a CPS contact or in response to the automated text reminder, after fully explaining this in the informed consent process. Despite the challenge to internal validity, providers will be informed as to which condition their patients are assigned, to allow them to integrate the mHealth intervention into their treatment plan. The PI informed healthcare teams of participants' engagement in the CPS interventions, barriers to adherence, and progress on improving adherence in a summary email at least every two weeks.

***Automated Text Reminders (ATR).*** The comparison condition will include automated text message reminders (ATR) modeled after an intervention used with a sample of AYA liver transplant patients, which was associated with increased adherence based on medication blood levels [14]. Specifically, text messages stated: "It's time to take your medicine! Please reply with any text." Texts were sent through automated survey invitations feature in REDCap, using Twilio. When participants enrolled, they selected the time(s) of day they preferred to receive their text reminders, and the PI checked their expressed preference against the electronic health record to confirm the frequency (i.e., once daily, twice daily) was consistent with their medication list. If participants confirmed receipt of at least 75% of their automated text reminders each month during the 12-week intervention, they received a \$40 gift card as an incentive. The PI informed healthcare teams of the frequency with which participants were confirming their automated texts in a summary email at least every two weeks.

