### **Intervention Training and Fidelity**

CPS interventions were delivered by 6 "adherence facilitators" or "coaches" who were undergraduate research students enrolled in experiential research course at University of

Southern California (either in Department of Psychology or Department of Preventive Medicine). Coaches underwent a background check and completed the CITI Human Subjects Protection course, TrojanLearn Mandated Reporter course, and Praesidium Social Media Safety course, as recommended by the USC Department of Risk Management and Insurance. Coaches participated in 2 4-hour training sessions to learn the intervention, involving a combination of lecture and role-plays with feedback. Coaches participated in weekly group supervision with the PI, and all calls and texts were recorded, uploaded via HIPAA-compliant REDCap file upload link, and reviewed by PI using a fidelity checklist. Coaches completed a short survey after each contact to record whether the participant answered their call or text, whether they reported taking their medication since the last call, topics covered in the call, and any referrals given. Additional details about the CPS intervention can be found in prior publications [3,4].

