### ***Primary Outcomes: Adherence Dependent Variables***

**Self-Reported Adherence.** In this study, medication adherence over the past 3 months was measured by a 3-item visual analogue scale (VAS) developed by Walsh, Dalton, and Gazzard (1998). The VAS uses percentage scales that contains the percent (%) value from 0 to 100 in which each point on the scale suggests the percent of time of medication adherence within a specified duration of time: 0% would mean “none of the time” or “never”; 50% would mean half of the time; 100% would mean “all of the time” or “always”, and numbers in between would mean amounts between “never” and “always” (Walsh, Dalton, & Gazzard, 1998). For each time frame, three visual analogue scales are provided, assessing 1) the percentage of the time patients took their medicine, 2) the percentage of the time patients took all the doses for the day, and 3) the percentage of the time patients took their medicine according to the directions (Walsh, Dalton, & Gazzard, 1998). Administering self-report adherence surveys by computer may decrease social desirability bias (Stirratt et al., 2015).

**MEMS Caps Adherence.** Participants (and caregivers, in the case of minor participants) will be oriented to using MEMS caps for one of the medications they take daily of their focal diagnosis (i.e., immunosuppressant for transplant, antiepileptic drug for epilepsy, hydroxyurea for sickle cell disease, metformin for type 2 diabetes). Microelectronic circuitry records the dates and times the caps are opened. We will calculate the percentage of prescribed doses that appear to have been taken through week 6, 12 and 18. MEMS caps are considered the “gold standard” in

adherence research and show moderate validity with both patient populations (Gerson et al., 2004; Cramer et al., 1995).

**Electronic Health Record Adherence Indicators.** Many of the focal diagnoses have regular labs collected as part of usual clinical care. For example, medication trough levels are usually collected periodically for the purpose of therapeutic drug monitoring for AYA living with solid organ transplants (i.e., immunosuppressant medications) and epilepsy (i.e., anti-epileptic drugs.). For other diagnoses, regularly collected labs are considered partially indicative of adherence, such as the hemoglobin A1C test for type 2 diabetes and mean corpuscular volume/fetal hemoglobin for sickle cell disease.

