Cell Phone Support to Promote Medication Adherence Among Adolescents and Young Adults With Chronic Illness

NCT04241627

8/8/2022

This randomized pilot trial tested three different digital health interventions against one another (CPS-C, n = 11, CPS-T, n = 12, and ATR, n = 11). We are interested in the impact on self-reported medication adherence. We have 6 different measures of dependent variables (VAS1w, VAS2w, VAS3w, VAS1m, VAS2m, VAS3m). We assessed our dependent variables 4 occasions, at 0 weeks (pre-tx), 6 weeks (mid-tx), 12 weeks (post-tx), and 18 weeks (follow-up). We would like to run mixed-effect models to test for intervention effects of 1) both CPS conditions (CPS-C and CPS-T, n = 23) versus ATR (n = 11); and 2) the CPS conditions against each other, ignoring ATR (CPS-C, n = 11 versus CPS-T, n = 12). I also have covariates (sex assigned at birth, diagnosis, age) that we can include during nested model building procedures, and include in final reported models if they lead to best fit.

Can we begin by examining the distributions of our dependent variables, and discuss whether we should use linear mixed-effects models; otherwise, we may need to transform or dichotomize the outcome or use a different type of model (poisson? Negative binomial?) to ensure model assumptions are met?

Then, can we evaluate the impact of missing data on my results by re-running these analyses using inverse probably weighting. It is possible that missing data will not be completely at random (i.e., participants with lower medication adherence may also be less likely to adhere to the online survey schedule).

Finally, I would like to calculate effect sizes for subgroups (see the final table). See tables on the next pages.

Blank Tables

Table 5

Best-Fitting Models Predicting Self-Reported Adherence for Both CPS Conditions (C and T) versus ATR (N = 34)

Dependent Variables	VAS1w			VAS2w			VAS3w			VAS1m			VAS2m			VAS3m		
	Estimates	CI	p															
Fixed Effects																		
Intercept																		
Time																		
Intervention Group (both CPS versus ATR)																		
Random Effects																		
σ^2																		
τ_{00}																		
τ_{11}																		
ρ_{01}																		
ICC																		
N																		
Observations																		
Marginal R ² / Conditional R ²																		
AIC																		

Note—Make ATR the reference group so the estimate tells us how the combined CPS groups compare

Table 6

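### Reporting on the VAS can differ by arm after allocation because only CPS participants are coached live, and the VAS-only SAP cannot separate this from a change in medicine taken

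*Protocol*

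**What the plan says.** **CPS arms.** Under Interventions, a coach is in contact by call or live text "between 3-5 days per week for 12 weeks". Under Intervention Training and Fidelity, the coach logs after each contact "whether they reported taking their medication since the last call". Care teams are told about engagement, "barriers to adherence, and progress on improving adherence in a summary email at least every two weeks". The Research Background gives the mechanism: "a positive bond with a credible, caring person creates a sense of accountability".

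**ATR arm.** The automated message asks for nothing about doses: "Please reply with any text". Care teams are told how often the texts were confirmed.

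**All arms.** Providers are alerted to nonadherence "whether disclosed in a CPS contact or in response to the automated text reminder, after fully explaining this in the informed consent process". Under Design, participants complete the pre-treatment questionnaires first and are then told their group, so baseline VAS precedes allocation and later VAS answers are given by people who know their arm.

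**Outcomes.** The protocol lists self-report, MEMS caps and health-record indicators together as primary adherence outcomes, and its Analytic Plan applies the VAS modelling approach to MEMS. On self-report bias it says "Administering self-report adherence surveys by computer may decrease social desirability bias". The SAP narrows the scope: "We are interested in the impact on self-reported medication adherence". It models six VAS variables and no MEMS outcome. Tables 5 and 6 have time and group as fixed effects, with no group-by-time term.

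**The concern.** For 12 weeks, two of the three arms repeatedly tell a person they are meant to feel accountable to whether they took their medicine. The third arm has no such exchange. An intervention that works through accountability may change what people take, what they say they take, or both. Over-reporting could rise in CPS, to please the coach or to stay consistent with what the coach was told. It could also fall, since regular talk about missed doses may make people more candid; the Research Background itself says that text contact tends to increase self-disclosure.

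Neither protection in the plan reaches this. Computer administration is the same in every arm, so it does not remove a difference between arms. Baseline VAS is measured before allocation, so adjusting for it cannot remove a shift that starts later.

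At stake is the meaning of the group coefficient in SAP Table 5 and the effect sizes in Tables 7 and 8. The protocol's Power Analysis section says the pilot is to supply effect sizes for future proposals. A reporting difference taken for a behavioural one would go straight into the design of the larger trial. The asymmetry bears mainly on CPS combined versus ATR; in CPS-T versus CPS-C both groups are coached and only the medium differs.

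**Working it through.** The plan gives no figure for reporting bias, so there is none to reproduce. The calculation below shows the scale of the risk; it does not estimate the bias.

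**Inputs from the documents.** 23 CPS v 11 ATR (SAP); four occasions at 0, 6, 12 and 18 weeks (SAP); ICC 0.5 (Power Analysis).

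**Assumptions, with no source in the documents.** VAS SD 20-25 points; two-sided 5% test; no true effect; constant differential over-reporting *b* of 5 or 10 points at each post-baseline visit; complete data; equal correlation between visits. Tables 5 and 6 also allow a random slope, which this simple form ignores.

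**1. Group main effect over four occasions (Table 5).** With no group-by-time term, the group coefficient averages the arm difference over all four visits. Baseline carries no bias, so the expected coefficient is 3/4 × *b*.

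- Variance factor for a mean of four: (1 + 3 × 0.5)/4 = 0.625.
- SE in SD units: √[(1/23 + 1/11) × 0.625] = √(0.1344 × 0.625) = 0.290.
- Non-centrality: 0.75*b*/SD ÷ 0.290, referred to a t distribution with 32 df.

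| *b* | SD | bias in *d* | non-centrality | rejection rate |
|---|---|---|---|---|
| 5 | 25 | 0.15 | 0.52 | 8% |
| 5 | 20 | 0.1875 | 0.65 | 10% |
| 10 | 25 | 0.30 | 1.04 | 17% |
| 10 | 20 | 0.375 | 1.29 | 24% |

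**2. Why the model matters.** Using the three post-baseline visits only, the variance factor is (1 + 2 × 0.5)/3 = 2/3, the SE is √(0.1344 × 2/3) = 0.299 and the bias is undiluted. The rates are then 10-13% for 5 points and 25-37% for 10. Those figures belong to a different analysis from the one in Table 5.

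**3. What a gap analysis could show.** Take the within-person difference between past-month VAS and MEMS percentage, averaged over weeks 6, 12 and 18, with ICC 0.5 again assumed. The 95% half-width for the arm difference is 2.037 × SD × 0.299, or 9.1, 12.2 and 15.2 points for a gap SD of 15, 20 and 25. Power to detect a 10-point arm difference in the gap is 58%, 37% and 25% respectively; for 5 points it is 19%, 13% and 10%.

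**4. Gap versus the plain MEMS contrast.** At SD 20 a MEMS contrast over the same visits has the same half-width, 12.2 points. If VAS and MEMS have equal SDs and correlation *r*, the gap variance is 2SD²(1 − *r*), which is below SD² only when *r* exceeds 0.5. The documents give no *r*. The gap therefore belongs beside the MEMS contrast and is no substitute for it.

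**The case against.** The strongest reply is that this is the usual limitation of self-report in an open behavioural trial, that live coach contact is the intervention itself, and that the protocol already has objective measures. Several parts of that reply stand.

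- **The alert rule is common to all arms.** A reader might infer that the promise to alert providers puts pressure on CPS participants alone. The text does not support that: the rule covers replies to automated texts as well, and all participants have it explained at consent. ATR participants can volunteer nonadherence, their confirmation rates also go to care teams, and they have a similar $40 incentive at about the 75% level.
- **The alert rule does not name the VAS.** Its two channels are coach contacts and text replies. A reader might also infer that participants are never told their VAS answers stay outside the alerts. The consent text is not in the documents reviewed, so nothing can be concluded about what it says.
- **Direction and size are unknown.** Coaching could increase candour, and week 18 falls six weeks after contacts end, when any shift may have faded.
- **The protocol's MEMS model is a natural check.** It weakens the point against the protocol but not against the SAP, which leaves MEMS out.
- **The gap is not a pure measure of reporting.** MEMS covers one focal-diagnosis medication, while the VAS asks about the patient's medicine generally, and cap use may itself differ by arm.

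What the reply does not remove is the difference in exposure after allocation, together with a SAP that has only self-report with which to judge it.

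**Conclusion.** The point holds as a risk to interpretation. The documents do not show that the VAS is biased. They show that coached and uncoached participants report under different conditions after allocation, and that the SAP has no outcome or analysis that could distinguish a change in reporting from a change in medicine taken. The argument rests on the difference in live contact and not on the provider-alert rule.

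Under the SAP's own four-occasion group effect, and given the assumed SD of 20-25 points, ICC of 0.5 and no true effect, the 5% error rate would become about 8-10% with 5 points of differential over-reporting and about 17-24% with 10. Greater candour in CPS would instead hide a true benefit. A gap analysis at N = 34 can reveal a large reporting difference but cannot rule out a modest one, so it cannot serve as a pass/fail test of a VAS result.

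**What to change.** In the SAP:

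1. Restore the protocol's MEMS model for the same two contrasts (CPS combined v ATR; CPS-T v CPS-C).
2. Add an exploratory mixed model, by arm, of the within-person gap: past-month VAS minus MEMS percentage over the matching days, at weeks 6, 12 and 18. Name in advance which past-month item is used. Cap openings are dated, so the matching window can be built from data the protocol already collects.
3. Report both with confidence intervals beside each VAS contrast. Describe a VAS difference as a difference in self-reported adherence unless the MEMS contrast supports it. State that a wide gap interval is not evidence that bias is absent.

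The cost is two models and no new data collection. The limits should be stated with the results: half-widths of about 9-15 points for an assumed gap SD of 15-25; one focal medication per participant; no planned baseline MEMS percentage, so the gap cannot be baseline-adjusted; only participants with cap data contribute; and arm differences in cap use could also move the gap.

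A change to consent or survey wording would come too late for this sample, since the SAP already reports achieved arm sizes. For the planned larger trial, the sponsor should confirm whether the consent text already says who sees VAS answers.
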